There are also some limitations on statistical analysis for subjects who enrolled into 233AS102 from 233AS101 Part C. Some subjects will be tofersen naïve and others will have received approximately 6 months of tofersen treatment prior to entry in 233AS102.

Analyses of efficacy and biomarker endpoints conducted for interim data (July 2021 and January 2022) highlighted the limitations of conducting standalone 233AS102 analyses in these endpoints as outlined below. Based on these learnings, it only makes sense to analyze the longitudinal data from 233AS102 for efficacy and biomarker endpoints as part of an integrated analysis of 233AS101 and 233AS102:

- In contrast to the prespecified integrated analyses of 233AS101 Part C and 233AS102, the standalone analyses of 233AS102 are based on data selected using post-randomization factors and therefore break the original randomization. On the other hand, the overall ITT analysis with the original 233AS101 Part C baseline provides an objective comparison of the two treatment regimens.

- Rate of progression is variable over time. Comparison of the treatment groups from 233AS102 fails to reflect the overall treatment effect due to early tofersen initiation that is evident in 233AS101 Part C. For example, if rate of progression is faster for the delayed start group in period 1 and then becomes comparable to the early start group, the comparison using only period 2 data would be misleading.
- There are imbalances at baseline of 233AS102, as expected due to the effect of tofersen in 233AS101 Part C, thus confounding interpretation of 233AS102 analyses.
- As described above, incorporation of baseline NfL as a covariate is the most objective mechanism to control for disease heterogeneity at baseline. However, baseline neurofilament in 233AS102 cannot be incorporated as a covariate due to the confounding effect of tofersen administration during 233AS102.

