3.5. Analysis Sets

ITT Population

The ITT population is defined as all subjects who enrolled and received at least one dose of study treatment in 233AS102.

Safety Population

The safety population is defined as all subjects who enrolled and received at least one dose of study treatment in 233AS102 (i.e. the overall ITT population of subjects).

Pharmacokinetic (PK) Population

The PK population is defined as all subjects who received at least one dose of study treatment and have at least one post-dosing PK concentration measurement in 233AS102.

Immunogenicity Population

The analysis population for immunogenicity is defined as all subjects who received at least one dose of study treatment and have at least 1 post-dosing sample evaluated for immunogenicity in 233AS102.

Populations used for analysis

Efficacy endpoints and PD/biomarker endpoints will not be summarized in 233AS102 standalone analysis and final CSR, but these data will be combined with data from 233AS101 and analyzed based on the ISE SAP.

The analysis of plasma and CSF PK concentration of tofersen will be analyzed using the PK population. All safety evaluations will be summarized using the safety population.

4. Statistical Methods for Planned Analyses

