Each hematology, blood chemistry, coagulation and CSF laboratory parameter will be flagged as “low” or “high” relative to the parameter’s normal range or as “unknown” if no result is available. For each urinalysis laboratory parameter, the number and percentage of subjects experiencing post-dosing shifts to abnormal will be summarized. For each hematology, blood chemistry, coagulation and CSF parameter, the number and percentage of subjects experiencing post-dosing shifts to ‘low’ or ‘high’ will be summarized. In each summary, the denominator for the percentage is the number of subjects at risk for the shift. The number at risk for the shift to low is the number of subjects whose baseline value was not low and who had at least one post-baseline value. The number at risk for the shift to high is the number of subjects whose baseline value was not high and who had at least one post-baseline value. Subjects will be counted only once for each parameter and each shift regardless of how many post-dosing assessments had that type of shift. Subjects with shift will be listed by laboratory parameter and shift type. All postbaseline data will be used in the shift tables, regardless of whether a scheduled or unscheduled visit. For CSF laboratory parameters, both tubes will be used in this assessment for the shift tables.

Summary statistics for actual values and change from baseline in laboratory values will be summarized by dose group and visit. Line plots for chemistry, hematology and CSF showing mean value for each dose group at each visit will also be presented.

To evaluate potential serious hepatotoxicity subjects with a post-baseline AST and/or ALT value ≥ 3 times the upper limit of normal (ULN) and a post-baseline bilirubin value >2 times ULN at any time, not necessarily concurrent, will be listed with their values. In addition, a plot will be presented with each subject’s maximum post-baseline AST or ALT value relative to the ULN against the subject’s maximum post-baseline bilirubin value relative to the ULN; values do not have to be concurrent. All postbaseline data will be used in the shift tables, regardless of whether a scheduled or unscheduled visit.

Listings of all chemistry, hematology, coagulation, CSF, urinalysis values and pregnancy test (serum and urine) will be provided. Abnormal values and potentially clinically significant values will be flagged.

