4.12. Immunogenicity Data

The immunogenicity population will be used for all analyses of immunogenicity data.

- For immunogenicity, the baseline value is defined as the latest immunogenicity data collected at any time prior to the first dose in 233AS102. If no immunogenicity data are collected immediately prior to the first dose in 233AS102, the baseline value is missing and will be imputed as anti-drug antibody negative for immunogenicity analyses.
- Subjects with at least one confirmed post-treatment positive result will be considered treatment-emergent positive for anti-drug antibodies if their baseline result is negative.
- Subjects where none of the post-treatment samples were positive for anti-drug antibodies will be considered negative regardless of their baseline result.
- For subjects who are confirmed positive at baseline and have at least one post-treatment sample with a ≥ 2 -fold increase in titer will be considered positive for anti-drug antibodies. Subjects that are positive at baseline, with subsequent post-treatment samples titers that are within 2-fold will be considered negative for anti-drug antibodies. If there

are any samples which the lab was able to confirm the screen was ADA positive but could not determine the magnitude of the positive response in time for interim datacut off date these will be considered as being ≥ 2 -fold for the purpose of this analysis.

Number and percentage of subjects who has positive result and negative result at baseline, subjects with any post-baseline positive result and negative result, subjects with any positive ADA will be summarized by prior treatment groups.

In addition, for subjects that are considered anti-drug antibody positive with immunogenicity data, the following may be evaluated:

- o Persistent anti-drug antibody response:
 - More than one positive time point that are ≥ 112 days apart
 - or
 - One or more positive time point, but < 112 days of evaluable data post first positive time point.
- o Transient anti-drug antibody response:
 - A single positive time point, followed by ≥ 112 days results which are all negative.

Or

- Two or more positive data points with < 112 days apart, with later negative samples that are ≥ 112 days apart from the first positive result.

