- o Caveat: Since the data are only being considered from baseline of 233AS102, a subject who became persistent in 101 will not be accounted for as persistent based on their prior data in 233AS101. Therefore, the subject could be summarized as being transient if there is no change in their titer in 233AS102.
- o If a subject has just one positive postbaseline ADA in 233AS102 at last available assessment at the time of Interim cutoff date and is still ongoing, then this subject will be summarized as transient.

Number and percentage of subjects who have persistent ADA result and transient ADA result will also be summarized by prior treatment groups.

The incidence of AEs selected by anaphylactic reaction SMQ, angioedema SMQ, and hypersensitivity SMQ will also be presented for subjects with at least 1 positive ADA result at post-baseline by prior treatment groups. Percentages will be calculated out of the immunogenicity population.

The incidence of AEs selected by anaphylactic reaction SMQ, angioedema SMQ, and hypersensitivity SMQ will also be presented for subjects with negative ADA result at post-

baseline by prior treatment groups. Percentages will be calculated out of the immunogenicity population.

5. Changes to Planned Analyses

- Analysis of efficacy, [REDACTED] and biomarker endpoints are specified in the Protocol; however, they will not be included in 233AS102 final CSR but will be included under the integrated analyses of 233AS101 and 233AS102. Analyses of efficacy and biomarker endpoints conducted for interim data (July 2021 and January 2022) highlighted the limitations of conducting standalone 233AS102 analyses in these endpoints as outlined in section 1. Based on these learnings, it only makes sense to analyze the longitudinal data from 233AS102 for efficacy and biomarker endpoints as part of an integrated analysis of 233AS101 and 233AS102. The analyses from 233AS102 baseline specified in the protocol will therefore not be appropriate and will not be conducted; analyses from other baseline definitions will be discussed in the ISE SAP.

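### Hypersensitivity-type AE percentages for ADA-positive and ADA-negative subjects share one denominator, so neither is an incidence within ADA status

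*SAP*

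**What the plan says.** SAP 4.12 (Immunogenicity Data) has two parallel paragraphs on the incidence of AEs selected by the anaphylactic reaction, angioedema and hypersensitivity SMQs. The first presents them for "subjects with at least 1 positive ADA result at post-baseline by prior treatment groups. Percentages will be calculated out of the immunogenicity population". The second "will also be presented for subjects with negative ADA result" after baseline, again by prior treatment group, and ends with the same sentence about percentages.

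SAP 3.5 (Analysis Sets) defines the immunogenicity population as dosed subjects who "have at least 1 post-dosing sample evaluated for immunogenicity in 233AS102". The result of that sample plays no part in the definition.

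SAP 4.12 also plans counts of "subjects with any post-baseline positive result and negative result, subjects with any positive ADA will be summarized by prior treatment groups". It gives a rule for negative status: "Subjects where none of the post-treatment samples were positive for anti-drug antibodies will be considered negative regardless of their baseline result". SAP 5 (Changes to Planned Analyses) and SAP 6.1 say nothing about the denominator.

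**The concern.** The evident purpose of paired ADA-positive and ADA-negative tables for these three SMQs is to see whether such events are more frequent in subjects who develop antibodies. That needs the incidence within each ADA status. With a denominator that mixes both statuses, each percentage also carries the size of its stratum. If ADA-positive subjects are a minority, their percentage is pulled down simply because they are few. A real excess could be hidden or reversed, and a difference could appear where none exists.

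Comparison across columns is affected as well. The ADA-positive share may differ between the prior-placebo and prior-tofersen columns, because some Part C subjects enter tofersen-naïve while "others will have received approximately 6 months of tofersen treatment prior to entry in 233AS102" (SAP 1). Equal risk among ADA-positives would then print as different percentages.

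**Working it through.** The plan gives no figure to reproduce, so the check is algebraic, followed by illustrations on assumed values.

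**Inputs from the documents.** Numerator 1: subjects with at least one positive post-baseline ADA result and an SMQ-selected event. Numerator 2: subjects with a negative post-baseline result and such an event. Denominator for both: the immunogenicity population, N, taken here within a prior-treatment column because the tables are presented that way.

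**Assumed, because the documents do not give them.** p = ADA-positive share of N; r1 and r0 = event risk among ADA-positive and ADA-negative subjects. The two groups are taken as complementary.

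**Formulas.**
- Printed ADA-positive percentage = (N·p·r1)/N = p·r1
- Printed ADA-negative percentage = (N·(1−p)·r0)/N = (1−p)·r0
- Printed ratio = (r1/r0) × p/(1−p)

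The factor p/(1−p) equals 1 only at p = 0.5. For a true ratio of 2, the printed ratio is 1 when p/(1−p) = 1/2, that is p = 1/3. Below that share the direction reverses.

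**True doubling, r1 = 20%, r0 = 10%.**

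| p | Printed ADA+ | Printed ADA− | Printed ratio (true 2.0) |
|---|---|---|---|
| 10% | 2.0% | 9.0% | 0.22 |
| 20% | 4.0% | 8.0% | 0.50 |
| 33% | 6.7% | 6.7% | 1.00 |
| 50% | 10.0% | 5.0% | 2.00 |
| 60% | 12.0% | 4.0% | 3.00 |

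**No true difference, r1 = r0 = 10%.** At p = 20% the tables print 2.0% and 8.0% (ratio 0.25). At p = 60% they print 6.0% and 4.0% (ratio 1.50).

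**In counts.** Take 50 subjects: 10 ADA-positive with 2 events and 40 ADA-negative with 4 events. The SAP rule gives 2/50 = 4% and 4/50 = 8%. Within status the figures are 2/10 = 20% and 4/40 = 10%, the opposite direction.

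**Across prior-treatment columns.** With r1 = 20% in both, the ADA-positive table prints 0.20 × 20% = 4% in a column with p = 20%, and 0.50 × 20% = 10% in a column with p = 50%.

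**If the groups overlap.** The SAP does not say that they are complementary. If the second group makes up a share s of N, its printed figure is s times the risk in that group, and the printed ratio is (r1/r0) × p/s. The factor p/(1−p) then no longer applies, but the figures are still joint percentages.

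**The case against.** The sentence might be read as naming only the analysis set, with the ADA subgroup as the implied denominator. That does not fit well. SAP 4.12 already opens by assigning the immunogenicity population to all its analyses, and the later sentence is specifically about percentages. A programmer would take it as the denominator.

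A common denominator can also be a deliberate descriptive choice: with complementary groups, the two percentages add up to the overall incidence. But the SAP gives no such rationale and calls the result incidence.

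The SAP does write out restricted denominators where it wants them. For laboratory shifts (SAP 4.9.2): "In each summary, the denominator for the percentage is the number of subjects at risk for the shift". The parallel is limited, because that rule removes subjects who cannot have the shift. It shows only that the plan states narrower denominators explicitly.

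The strongest objection concerns weight, and much of it stands. The tables are descriptive and no comparison between them is planned. The primary AE and SAE tables use the safety population and are unaffected. The planned count of subjects with any positive post-baseline result matches the first table's stratum, so its incidence can be recovered by one division if event counts are printed. Recovery is less certain for the second table. A subject may have both positive and negative results. SAP 4.12 also has a titre rule that classes some baseline-positive subjects as negative although they may have positive post-baseline samples.

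**Conclusion.** The concern holds. As written, both tables give joint percentages of event and ADA status under the name of incidence, and this follows from the text without any numerical assumption. The size depends on the ADA-positive share and the event risks, which the documents do not give. Under an assumed true doubling (20% against 10%) and complementary groups, the printed ratio runs from 0.22 at a 10% ADA-positive share to 3.00 at 60%, and is right only at 50%. The consequence is confined to reading two descriptive safety tables. No test, sample size or primary endpoint depends on them. It is a modest point, but it should be corrected because the stated rule can hide, reverse or create an apparent association between ADA and hypersensitivity.

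**What to change.** Replace the denominator sentence in each of the two paragraphs of SAP 4.12.

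- ADA-positive table: *Within each prior treatment group, the denominator is the number of subjects in the immunogenicity population who have at least one positive post-baseline ADA result.*
- ADA-negative table: *Within each prior treatment group, the denominator is the number of subjects in the immunogenicity population who have no positive post-baseline ADA result.*

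Select the subjects for the second table by the same condition, so that the strata are mutually exclusive and together make up the immunogenicity population. This keeps the rule that the first paragraph already uses and takes its complement from the existing none-positive rule. The 2-fold titre rule should not be used to move subjects between these two tables, and the SAP should say so.

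The cost is two SAP sentences and a changed denominator in two tables, with no new data. The change does not adjust for follow-up time, nor for whether the AE came before the positive ADA result.

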6.1. Changes in Version 4.0

- Updated schedule of activities and the corresponding text changes to align with protocol amendment V6.0; added a summary of protocol amendments
- Added demographics and baseline disease characteristics tables for final CSR.
- Removed ALSFRS-R, SVC, HHD analyses which will be analyzed in ISE SAP.
- Removed PD/biomarker endpoint analyses which will be analyzed in ISE SAP.
- Removed the subgroup of ‘enriched’ and ‘other’.
- Removed type of visit summary by endpoint.

7. References

Appendix B: Derivation of C-SSRS

The Columbia Suicide Severity Rating Scale (C-SSRS) is an assessment that evaluates suicidal ideation and behavior. C-SSRS measurements are collected with respect to “Lifetime: time he/she felt most suicidal” at baseline, and with respect to “Since last visit” at last visit (Day 57 for Part A and Day 169 for Part B) and ET visit.

There are 11 common “Yes/No” questions at baseline and postbaseline visits. Five questions on suicidal ideation and five questions on suicidal behavior are re-ordered and follow increasing severity order respectively as shown in **Table 8**. In particular, only patients who answered “Yes” to question 2 will proceed to question 3, 4 and 5. Thus, for any subjects who answered “No” to question 2, an answer “No” will also be assumed to question 3, 4, and 5. An additional “Yes/No” question is used to record if subject had committed suicide in postbaseline visits.

Table 8: C-SSRS re-ordered questions

Suicidal Ideation	
Question 1	Wish to be dead
Question 2	Non-specific active suicidal thoughts
Question 3	Active suicidal ideation with any methods (not plan) without intent to act
Question 4	Active suicidal ideation with some intent to act, without specific plan
Question 5	Active suicidal ideation with specific plan and intent
Suicidal Behavior	
Question 6	Preparatory acts or behavior
Question 7	Aborted attempt
Question 8	Interrupted attempt
Question 9	Actual attempt
Question 10	Suicidal behavior
Question 11 (postbaseline visit only)	Suicide
Self-Injurious Behaviour without Suicidal Intent	
Question 12	Self-injurious behavior without suicidal intent

A subject is considered to have *suicidal ideation* at the period of interest if a “Yes” is answered to any of the five suicidal ideation questions (Question 1-5). A subject is considered to have *suicidal behavior* at the period of interest if a “Yes” is answered to any of the five suicidal behavior questions (Question 6-10) at baseline or a “Yes” is answered to any of the six suicidal behavior questions (Question 6-11) at postbaseline visit.

A subject’s *Suicidal Ideation Score* is defined as the maximal suicidal ideation question number (maximal of 1-5) with an answer “Yes” per visit. The score is defined as 0 if the subject answered “No” to all 5 Suicidal Ideation questions at that visit. A subject is considered to have treatment-emergent suicidal ideation if the subject had either new or worsening suicidal ideation. A subject is considered to have new suicidal ideation if the subject’s Suicidal Ideation Score increased at postbaseline visit compared to a score 0 at baseline. A subject is considered to have worsening suicidal ideation if the subject’s Suicidal Ideation Score increased at postbaseline visit compared to a positive score at baseline.

A subject is considered to have treatment-emergent suicidal behavior if the subject answered “Yes” to any suicidal behavior questions at any postbaseline visit while answered “No” to all suicidal behavior questions at baseline.

Signature Page

Document Name: BIIB067_233AS102_SAP_Final_V4.0

Document Title:

Signed by	Role	Date / Time (UTC)
[REDACTED]	Signing as Approver	06-Aug-2024 06:26:08
[REDACTED]	Signing as Approver	05-Aug-2024 15:55:01
[REDACTED]	Signing as Approver	05-Aug-2024 16:49:09
[REDACTED]	Signing as Approver	05-Aug-2024 14:22:24

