8.2. Exclusion Criteria

Candidates will be excluded from study entry if any of the following exclusion criteria exist at Screening, or at the timepoint specified in the individual criterion listed:

CONFIDENTIAL

The information contained herein may not be used, disclosed, or published without the written consent of Biogen MA Inc.

Medical History

1. History of drug abuse or alcoholism within 6 months before study enrollment that would limit participation in the study, as determined by the Investigator.
2. Presence of an untreated or inadequately treated active infection requiring systemic antiviral or antimicrobial therapy, or any other ongoing medical condition during the screening period that, according to the Investigator, would interfere with the conduct or assessments of the study.
3. Significant cognitive impairment, clinical dementia, or unstable psychiatric illness, including psychosis, suicidal ideation, suicide attempt, or untreated major depression ≤ 90 days, as determined by the Investigator.
4. History of allergies to a broad range of anesthetics.
5. Presence of risk for increased or uncontrolled bleeding and/or risk of bleeding that is not managed optimally and could place a participant at an increased risk for bleeding during or after an LP procedure. These risks could include, but are not limited to, anatomical factors at or near the LP site (e.g., vascular abnormalities, neoplasms, or other abnormalities) and underlying disorders of the coagulation cascade, platelet function, or platelet count (e.g., hemophilia, Von Willebrand's disease, liver disease).
6. Presence of an implanted shunt for the drainage of CSF or an implanted CNS catheter.
7. Clinically significant abnormalities in hematology or clinical chemistry parameters, as determined by the Investigator, which would render the participant unsuitable for enrollment.
8. Clinically significant, as determined by the Investigator, 12-lead ECG abnormalities, including corrected QT interval using Fridericia's correction method of > 450 ms for males and > 470 ms for females.

Medications

9. Prior or current treatment with small interfering RNA, stem cell therapy, or gene therapy.
10. Treatment with another investigational drug, biological agent (excluding BIIB067), or device within 1 month or 5 half-lives of study agent, whichever is longer.
11. Current or anticipated need, in the opinion of the Investigator, of a DPS during the study period.

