4.9.7. Columbia Suicide Severity Rating Scale (C-SSRS)

The details of derivation and imputation for C-SSRS is described in Appendix B. The following analyses on C-SSRS measurements will be conducted:

- Descriptive summary of subjects who answered “Yes” to any question 1-12 as well as subjects who had suicidal ideation or suicidal behavior at baseline and at any post-baseline visit. The denominator for baseline summary is the number of subjects who were dosed and had baseline assessment; the denominator for post-baseline summary is the number of subjects who were dosed and had at least one post-baseline assessment for each question.
- Descriptive summary of subjects who had treatment-emergent suicidal ideation, subjects who had new suicidal ideation as well as subjects who had worsening suicidal ideation. The denominator is the number of dosed subjects with both baseline and at least one post-baseline suicidal ideation assessment.
- Descriptive summary of subjects who had treatment-emergent suicidal behavior. The denominator is the number of subjects who answered “No” to all suicidal behavior questions at baseline and had at least one post-baseline suicidal behavior assessment.

Listing of subjects having treatment-emergent suicidal ideation will be provided. Subjects who had new suicidal ideation and subjects who had worsening suicidal ideation will be flagged. The listing will display both baseline and post-baseline Suicidal Ideation Scores for each subject. Listing of subjects having treatment-emergent suicidal behavior will also be provided.

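### New and worsening suicidal ideation arise from separate baseline groups but share one all-assessed denominator, so their percentages depend on each study group's baseline ideation share

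*SAP*

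**What the plan says.** SAP Appendix B sets a subject's ideation score at each visit as the "maximal suicidal ideation question number (maximal of 1-5") answered Yes, or 0 if all five answers are No. Two kinds of treatment-emergent ideation follow:

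- new: "Suicidal Ideation Score increased at postbaseline visit compared to a score 0 at baseline";
- worsening: "Suicidal Ideation Score increased at postbaseline visit compared to a positive score at baseline".

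SAP 4.9.7 summarizes treatment-emergent, new and worsening ideation in one bullet with one denominator: "The denominator is the number of dosed subjects with both baseline and at least one post-baseline suicidal ideation assessment".

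Two other places restrict the denominator to subjects who could have the event. The next bullet of 4.9.7 counts treatment-emergent suicidal behavior only among subjects who answered No "to all suicidal behavior questions at baseline and had at least one post-baseline suicidal behavior assessment". SAP 4.9.2 says of laboratory shifts that "the denominator for the percentage is the number of subjects at risk for the shift", and defines the at-risk number separately for shifts to low and to high.

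Appendix B says that the baseline form asks about "Lifetime: time he/she felt most suicidal". Protocol 8.2 excludes some recent psychiatric illness, as judged by the investigator, "including psychosis, suicidal ideation, suicide attempt, or untreated major depression ≤ 90 days". It does not exclude a lifetime history of ideation.

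**The concern.** A subject with baseline score 0 cannot worsen, and a subject with a positive score cannot have new ideation. With the common denominator, each is counted as event-free in a row where no event was possible. The worsening percentage then mixes two quantities: how many subjects had ideation at baseline, and how often such subjects got worse.

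Safety summaries are presented by study group (SAP 3.2 and 4.9). If the groups differ in baseline ideation, their new and worsening percentages differ even when the underlying risks are equal. Worsening among subjects with prior ideation is of particular clinical interest, and it would appear as a small percentage whenever prior ideation is uncommon. In the same C-SSRS output, the behavior percentage has an at-risk base and these two ideation percentages do not.

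**Working it through.** The SAP states no rate or expected count on this point, so there is no figure to reproduce.

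**Inputs.** From Appendix B: scores run 0 to 5; new requires baseline 0; worsening requires a positive baseline, in effect 1 to 4. From 4.9.7: the common denominator, N. Not in the documents, so assumed: p, the share of N with a positive baseline score, and the event risks below.

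**Formulas** (ignoring baseline score 5). Let w be the risk of worsening among subjects with a positive score, and v the risk of new ideation among those with score 0.

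- Printed worsening % = p × w, so the dilution factor is 1/p.
- Printed new % = (1 − p) × v, so the dilution factor is 1/(1 − p).
- Printed treatment-emergent % = p × w + (1 − p) × v, the overall risk among all assessed subjects.

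**Range over p**, with w = v = 10% as an illustration:

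| assumed p | factor, worsening | printed worsening | factor, new | printed new |
|---|---|---|---|---|
| 5% | 20 | 0.5% | 1.05 | 9.5% |
| 10% | 10 | 1.0% | 1.11 | 9.0% |
| 20% | 5 | 2.0% | 1.25 | 8.0% |
| one third | 3 | 3.3% | 1.50 | 6.7% |
| 50% | 2 | 5.0% | 2.00 | 5.0% |
| 60% | 1.67 | 6.0% | 2.50 | 4.0% |

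**Two groups with equal risk.** With w = 25% in both, a group with p = 40% prints 0.40 × 25% = 10%, and a group with p = 10% prints 0.10 × 25% = 2.5%. The gap comes only from p.

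**A worked table.** Take N = 183, the maximum dosed in Study 233AS101 (SAP 2.5), as an upper bound only. Assume 37 subjects with a positive baseline score (about 20%), 5 worsening and 10 new.

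- Worsening: 5/183 = 2.7% as planned; 5/37 = 13.5% at risk.
- New: 10/183 = 5.5% as planned; 10/146 = 6.8% at risk.
- Treatment-emergent: 15/183 = 8.2%.

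**Baseline score 5.** If a share q of N is at score 5, the exact factors are 1/(p − q) for worsening and 1/(1 − q) for the combined row. With q assumed at 2% and p at 20%, these are 1/0.18 = 5.6 and 1/0.98 = 1.02. The combined row barely moves.

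**The case against.** The case for the present text is substantial.

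- **The percentage is correctly computed for what it is.** It is the proportion of all assessed subjects whose ideation worsened. It is too low only if read as a risk among those with prior ideation, which 4.9.7 does not claim. This stands: the point is about interpretation, not an arithmetic error.
- **The common denominator is coherent.** Treatment-emergent ideation is new or worsening, so the two rows add up to the combined row, where nearly everyone is at risk. This stands, and is a reason to keep that denominator for the combined row.
- **There is no SAP-wide at-risk rule to break.** A reader might infer that the ideation rows violate a general convention. The behavior denominator follows from its own definition, which has no worsening category, and SAP 4.12 divides adverse events in antibody-positive and antibody-negative subjects by the whole immunogenicity population. What remains is a contrast with two specific sections. The laboratory rule is the closer parallel, because it too splits one parameter into two shifts with separate risk sets.
- **Other outputs help.** The first bullet of 4.9.7 tabulates ideation at baseline, and the listing flags new and worsening subjects and shows their scores. At-risk rates can be approximated, but not recovered exactly: the baseline tabulation does not require a later assessment, and the listing covers only subjects with treatment-emergent ideation.
- **The consequence is limited.** This is a descriptive safety table, and the SAP attaches no test or decision rule to it. Risk sets may be tiny: 183 over three groups is about 61 each, and p = 10% leaves about 6 at risk of worsening, so one subject moves the row by about 17 points. This stands, and is why n/N should be printed.

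**Conclusion.** The point holds for two sub-rows of a descriptive safety table. As planned, the new and worsening percentages are (1 − p) and p times their at-risk values, apart from baseline score 5, and are not comparable between study groups whose p differs. That follows from the SAP's definitions and needs no assumption.

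The size does need one. A reader might infer that worsening is diluted several-fold as a matter of fact. The documents do not support that, because they give no p. The factor is 3 or more only if p is about one third or less, and 2 or less if p is 50% or more. The lifetime baseline form may bring in remote ideation that the 90-day exclusion does not remove, so p cannot be narrowed from the text.

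A reader might also infer that overall treatment-emergent ideation is understated. It is not, beyond the few subjects who may start at score 5.

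**What to change.** In SAP 4.9.7, keep the common denominator for overall treatment-emergent ideation. Report new ideation as n/N (%) among subjects with baseline score 0, and worsening as n/N (%) among subjects with baseline score 1 to 4, each also requiring at least one post-baseline ideation assessment. Appendix B can stay as it is.

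The cost is one sentence in the SAP and a denominator change in one table, using data already collected. There are two drawbacks. N in the worsening row may be small, which printing n/N makes visible. The two sub-row percentages will no longer add up to the overall percentage, although the counts still will; a table footnote can say so.
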